13.10.5 Serious Adverse Events

An SAE is an AE that leads to any of the following medical occurrence:

- Results in death
- Is life-threatening, meaning the patient is at risk of death at the time of event
- Requires hospitalization or prolongation of existing hospitalization. Emergency room visits that do not result in admission to the hospital should not be considered as a SAE requiring hospitalization or prolongation of existing hospitalization, and such emergency room visits should be evaluated for one of the other serious outcomes instead
- Results in disability/incapacity
- Is a congenital anomaly/birth defect
- Events requiring medical and/or surgical intervention to prevent one of the other outcomes listed in the definition above or, based on medical and/or scientific judgment of investigator, are important and should be considered serious

Any hospitalization only for the purpose of diagnostic or study-related procedures is not to be considered as a serious AE.

Any SAE, including death from any cause that occurred during the study, whether or not related to the study drug, must be reported to the Safety Desk immediately (within 24 hours) via telephone, fax, or e-mail. If initially reported via telephone or e-mail, this must be followed up by a written report to be submitted within 24 hours of its occurrence.

Serious Adverse Event Reporting

ICON Clinical Research

Medical & Safety Services

United States of America - Serious Adverse Event Reporting

[contact]

[contact]

e-mail: [contact]

Taiwan - Serious Adverse Event Reporting

[contact]

[contact]

e-mail: [contact]

It is imperative to report the SAE within 24 hours of its occurrence so that reporting to the Regulatory Agencies can be met within the required time frame (7 or 15 calendar days). Because of the need to report to health authorities all SAEs in a timely manner, it is vitally important that an investigator report immediately any AEs that would be considered serious, even if the PI does not consider the AE to be clinically significant or drug-related. Should the PI become aware of an SAE (regardless of relationship to study drug) that occurs within 30-days after stopping the study drug, the SAE must be reported in accordance with the procedures specified in this protocol. There is no time limit on the collection of SAEs that are considered related to study drug. All SAEs that are not resolved by the end of the study, or that were not resolved upon discontinuation of the patient's participation in the study, are to be followed until either: the AE resolves, the AE stabilizes, the AE returns to baseline values (if a baseline value is available), or it is shown that the AE is not attributable to the study drug or study conduct. Medical and scientific judgment is to be exercised in deciding whether expedited reporting is appropriate in other situations, such as for important medical events that were not immediately life-threatening or did not result in death or hospitalization but are jeopardizing the patient or require intervention to prevent one of the outcomes listed above.

13.10.6 Pregnancy

Patients with child-bearing potential must be confirmed as not being pregnant at Screening and willing to use effective methods of contraception during the study and for 3 months after the last dose of study drug (as defined in [Section 9.3.1](#), Inclusion Criterion 16). Following administration of study drug, pregnancy cases in any female patient will be reported if known until the patient completes or withdraws from the study. The pregnancy will be reported immediately by phone and by faxing a completed Pregnancy Report to the sponsor (or designee) within 24 hours of knowledge of the event. The pregnancy will not be processed as an SAE; however the investigator will follow the patient until completion of the pregnancy and must assess the outcome in the shortest possible time but not more than 30 days after completion of the pregnancy.

The investigator should notify the sponsor (or designee) of the pregnancy outcome by submitting a follow-up Pregnancy Report. If the outcome of the pregnancy meets the criteria for immediate classification of an SAE (e.g., spontaneous or therapeutic abortion [any congenital anomaly detected in an aborted fetus is to be documented], stillbirth, neonatal death, or congenital anomaly), the investigator will report the event by phone and by faxing a completed SAE form to the sponsor (or designee) within 24 hours of knowledge of the event.

14 STATISTICAL EVALUATION

14.1 Sample Size and Power

The study uses a two-stage design. Thirty evaluable patients (15 in each stratum) will be treated initially (Stage 1), with expansion to a maximum of 60 evaluable patients (Stage 2). Enrollment will continue until the target number of evaluable patients has been enrolled.

The statistical design is based on literature published by Green and Dahlberg (1992)³⁰, von Mehren et. al. (2012)³¹ and Hoang et. al. (2013)³². It is assumed that within each of the KRAS tumor mutation positive and negative strata, a PFS rate at 12 weeks of 40% and 35% overall (unselected) population will be of interest. Further testing will not be pursued if the PFS rate at 12 weeks is less than 15%.

Initially, 15 evaluable patients are to be accrued within each stratum. If two or more patients are alive and progression-free at Week 12 within a stratum, then an additional 15 evaluable patients will be accrued to that stratum for a total of 30 evaluable patients. If nine or more patients are alive and progression-free at Week 12 within the 30 evaluable patients in the stratum then antroquinonol will be considered worthy of further study in that cohort. This design will allow a significance level of 2.8% and a power of 90.5% within each stratum.

In addition to within-stratum hypothesis testing, this study is also designed to investigate the PFS rate at 12 weeks in the overall (unselected) population. If less than three patients are alive and progression-free at Week 12 in the first 20 evaluable patients, and the criterion for continuing the individual stratum are not met, then the accrual for all strata will be discontinued. Otherwise, a maximum of 40 additional evaluable patients will be entered (depending on whether any individual stratum is closed). Fifteen or more patients alive and progression-free at Week 12 out of the maximum 60 evaluable patients would warrant further study. The overall design has a significance level of 2.8% (probability of falsely declaring the regimen with a 15% PFS rate at 12 weeks to warrant further study) and power 95.6% (probability of declaring the regimen with a 35% PFS rate at 12 weeks in the overall population to warrant further study).

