8 STUDY OBJECTIVES

8.1 Primary Objective

To evaluate the activity of antroquinonol in unselected, KRAS-positive, and KRAS-negative patients with stage IV (including pleural effusion) non-squamous NSCLC who have failed two lines of anti-cancer therapy.

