Patients will attend study visits on Days 0, 14, 28, 42, 56 and 84 during the first 12-week treatment cycle, every 4 weeks during the second, third, and fourth treatment cycles (Extension Phase); and every 12 weeks during subsequent treatment cycles (Extension Phase). The study-specific procedures include: physical examination, vital signs, 12-lead ECG, performance status, clinical laboratory tests, AEs, concomitant medication and patient compliance. The schedule of assessments is presented in [Table 9.1](#).

Patients discontinuing study drug will attend an End of Study (EOS) Visit, 4 weeks after the last administration of study drug. In the event that a patient is scheduled to start a new treatment earlier than 3 weeks after the last dose of study drug, the EOS Visit should occur before the start of the new treatment and the reason documented.

Intensive PK sampling will be performed on Days 0 and 28 in all patients enrolled in Stage 1. Sparse PK sampling will be performed on Days 28, 42, and 56 in all patients enrolled in Stage 2.

All patients who withdraw from the study drug, but consent to be followed up for survival status, will be followed up by telephone contact every 3 months, for a maximum of 6 months from the date of last administration of study drug or death, whichever occurs first.

Tumor assessments will be performed at Screening, Days 42 and 84 using the Response Evaluation Criteria in Solid Tumors (RECIST) criteria, version 1.1 (see [Appendix 1](#)). Tumor assessments will be performed every 12 weeks during the Extension Phase.

The primary efficacy endpoint is progression-free survival (PFS) rate at 12 weeks, which is defined as the proportion of patients alive and progression-free at Week 12. Patients will be progression-free if they have no evidence of progressive disease (defined according to RECIST guidelines, version 1.1) from the start of treatment to Week 12.

The study uses a two-stage design seeking to detect a true PFS rate of more than 35% in the overall (unselected) population and 40% within the KRAS tumor mutation positive and negative strata. Thirty evaluable patients (15 in each stratum) will be treated initially (Stage 1), with expansion to a maximum of 60 evaluable patients (Stage 2). The rules for continuing the overall study and individual stratum are provided in [Section 14.2](#).

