14.2.2.1 Primary Efficacy Analysis

The primary endpoint is the PFS rate at 12 weeks, defined as the proportion of patients alive and progression-free at Week 12. Patients will be progression-free if they have no evidence of progressive disease (defined according to RECIST guideline, version 1.1) from the start of treatment to Week 12. An evaluable patient who died from any cause or discontinued the study for any reason without a post-screening or Week 12 tumor assessment will be considered as failing to respond to treatment.

The primary analysis will be performed on the evaluable population as defined in [Section 14.2.1](#). The FAS and PPS (as defined in [Section 14.2.1](#)) will be used for supportive efficacy analyses. The PFS rate together with a two-sided 95% exact confidence interval (CI) will be calculated for the evaluable population, FAS and PPS.

The primary analysis will follow the two-stage procedure as specified in [Section 14.1](#).

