14.3 Interim Analysis

An interim analysis for safety and efficacy will be performed when 20 patients overall and when 15 patients within each stratum are evaluable for the primary endpoint, PFS rate at 12 weeks. As described in [Section 14.1](#), if less than two patients are alive and progression-free within a stratum, then the accrual for that stratum will be discontinued. Otherwise, a maximum of 15 additional evaluable patients will be accrued to that stratum for a total of 30 evaluable patients. Furthermore, if less than three patients in the overall

(unselected) population are alive and progression-free in the first 20 evaluable patients, and the criterion for continuing the individual stratum are not met, then the accrual for all strata will be discontinued. Otherwise, a maximum of 40 additional evaluable patients will be entered (depending on whether any individual stratum is closed).

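### The overall 2.8% and 95.6% belong to a simpler 20/60 rule; as written, the 20-patient stop is ambiguous and no overall pass mark is given once a stratum closes

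*Protocol*

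**What the plan says.** The primary objective (Section 8.1) is "To evaluate the activity of antroquinonol in unselected, KRAS-positive, and KRAS-negative patients with stage IV" disease, so the unselected population is one of three groups to be judged. Section 14.2.2.1 ties the primary analysis to the design section: "The primary analysis will follow the two-stage procedure as specified in" Section 14.1.

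Section 14.1 sets two layers of rule.

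- **Stratum.** Enrol 15. With two or more successes (alive and progression-free at Week 12), enrol 15 more. Nine or more of 30 is a pass. Stated significance level 2.8%, power 90.5% at a 40% rate.
- **Overall.** All accrual stops if fewer than three patients succeed among the "first 20 evaluable patients, and the criterion for continuing the individual stratum are not met, then the accrual for all strata will be discontinued". Section 14.3 then says "Otherwise, a maximum of 40 additional evaluable patients will be entered (depending on whether any individual stratum is closed"). The pass mark is "Fifteen or more patients alive and progression-free at Week 12 out of the maximum 60 evaluable patients would warrant further study". The stated significance level is 2.8% at a 15% rate, with "power 95.6% (probability of declaring the regimen with a 35% PFS rate at 12 weeks in the overall population to warrant further study").

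Section 14.3 places looks at 20 patients overall and at 15 per stratum, and repeats that fewer than two successes closes a stratum. The synopsis carries the same rules. Section 9.1.1 says "The rules for continuing the overall study and individual stratum are provided in" Section 14.2, but Section 14.2.2.1 only points back to 14.1.

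**The concern.** The overall figures are offered as properties of the whole design, yet a design that can close a stratum at 15 does not always reach 60 patients. Two things are left open.

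1. **The joint stopping condition.** The text does not say whether the stratum criterion is unmet when one stratum fails or only when both do, nor whether it is judged at 20 patients or at 15 per stratum. With 20 patients in total, at most one stratum can have its 15.
2. **The pass mark at 45 patients.** If one stratum closes and the other goes on to 30, the total is 15 + 30 = 45. The only overall mark is tied to the maximum of 60.

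At stake is the unselected conclusion. If the mark for 45 patients is settled after the data are seen, the error rate depends on that choice. The first point also decides how readily the whole trial stops when the drug is inactive.

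**Working it through.** **Inputs** (all Section 14.1): null rate 15%; rate of interest 40% per stratum and 35% overall; stratum rule 15 + 15, continue at ≥2, pass at ≥9; overall rule stop at <3 of 20, pass at ≥15 of 60. The two strata are taken as independent and all calculations are exact binomial.

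**Step 1: the printed figures.**

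Stratum: Σ over x ≥ 2 of P(Bin(15,p) = x) · P(Bin(15,p) ≥ 9 − x) gives 0.0276 at p = 0.15 and 0.9049 at p = 0.40. Both are as printed.

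Overall, ignoring stratum closure: Σ over x ≥ 3 of P(Bin(20,p) = x) · P(Bin(40,p) ≥ 15 − x) gives 0.0279 at p = 0.15 and 0.9558 at p = 0.35. Both are as printed, so the printed pair is that of a stand-alone 20/60 rule.

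**Step 2: how often 45 patients arises.** A stratum closes with probability q = P(Bin(15,p) ≤ 1): 0.3186 at 15%, 0.0142 at 35%, 0.0052 at 40%. Exactly one closes with probability:

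- 15%/15%: 2 × 0.3186 × 0.6814 = 0.434
- 35%/35%: 2 × 0.0142 × 0.9858 = 0.028
- 40%/15%: 0.3186 × 0.9948 + 0.0052 × 0.6814 = 0.320

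**Step 3: the rule with closure and no effective 20-patient look.** Pass probability = P(60 patients, total ≥15) + P(45 patients, total ≥ mark). The first term is 0.0266 at 15% and 0.9427 at 35%.

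| Mark at 45 | Significance level | Power at 35% |
|---|---|---|
| no pass possible | 0.0266 | 0.9427 |
| 15 | 0.0266 | 0.9461 |
| 12 | 0.0281 | 0.9562 |
| 11 | 0.0316 | 0.9604 |
| 10 | 0.0411 | 0.9642 |

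A mark of 12 of 45 would make the printed pair true, but the protocol does not state it.

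**Step 4: the readings of the joint stop, with 15 kept as the bar.** Ranges cover splits of the first 20 from 5/15 to 10/10.

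| Reading | Significance level | Power at 35% | Stop all accrual at 15% |
|---|---|---|---|
| Both strata fail, judged at 15 each | 2.7% | 94.6% | 10.1% |
| Either fails, judged at 15 each | 2.7% | 94.6% | 33.6–34.7% |
| Both fail, judged at 20 | 2.6–2.7% | 94.2–94.6% | 26.6–29.6% |
| Fewer than 3 of 20 as a hard stop | 2.6% | 94.0–94.2% | 40.5% |

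Two readings make part of the sentence idle. If both strata must fail at 15, there are at most 1 + 1 = 2 successes, so fewer than 3 of 20 follows automatically and the look adds nothing. If either failing counts and is judged at 20, fewer than 3 successes cannot give two in each stratum, so the stratum clause adds nothing and the look is a hard stop.

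**Step 5: what the missing mark can change.** A closed stratum contributes at most 1 success, so a pooled total of 10 or more at 45 patients already means at least 9 in the open stratum. The mark therefore affects only the unselected conclusion, not whether any go is declared. As an illustration, with true rates of 40% and 15% the chance of an unselected go is 54.5% with no pass possible at 45, 62.6% with mark 15, and 75.8% with mark 12.

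**The case against.** Read as a whole, Section 14.1 arguably leaves one sensible reading. A stratum with two or more successes must expand, so stopping everything because only one stratum fails would contradict that rule. A hard stop ignores the joining clause. Judging a 15-patient criterion at 20 patients overall has no support in the text. That leaves both strata failing at 15. On this view, fifteen or more of the maximum 60 can be taken as a fixed bar whatever the final number, giving a single answer of 2.7% and 94.6%. The printed power is then only 1.0 point too high, the significance level is slightly lower than printed, and 45 patients arises in just 2.8% of trials at 35%. The 40%/15% scenario is not one of the protocol's hypotheses. The monitoring committee charter or the SAP might hold operating details.

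Much of this stands. The both-strata reading is the most natural, and the effect on power is modest. But even that reading does not give the printed power, makes the 20-patient look in Section 14.3 redundant, and only infers the bar at 45. The 40%/15% case is illustrative, though Section 9.2.1 itself expects that KRAS-positive patients may benefit more. A charter or SAP can supply detail, but cannot make true a power figure that the protocol prints for a different rule.

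**Conclusion.** The concern holds. The binomial arithmetic behind the printed figures is right, but it is attached to the wrong rule. With 15 kept as the bar, overall power is overstated by 1.0 to 1.6 points (95.6% against 94.0% to 94.6%); if no unselected pass is possible at 45, power is 94.3%. The significance level is slightly conservative in all of these cases. The design is not underpowered and the stratum conclusions are unaffected.

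The larger weakness is that the unselected decision is undefined in a case arising in 43% of trials at the null rate. A mark of 10 or 11 chosen afterwards would raise the overall significance level to 4.1% or 3.2%. These results assume independent strata, a common rate in both strata for the significance level and power, and full accrual to the stated sizes. The point should be corrected, but it does not put the trial's main conclusions at risk.

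**What to change.** In Sections 14.1 and 14.3 and the synopsis:

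1. State whether the 20-patient look acts alone or is dropped. If the joint condition is kept, say whether one or both strata must fail and at what point this is judged.
2. State the overall pass mark when one stratum has closed, or that no unselected conclusion is then drawn.
3. Restate the overall significance level and power for the rule chosen.

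Without the look, the options are: keep 15 (2.7%/94.6%); draw no unselected conclusion at 45 (2.7%/94.3%); or use 12 of 45 (2.8%/95.6%). The last recovers the printed figures but makes an unselected go easier after a stratum has failed, so the choice is the sponsor's. Correct the cross-reference in Section 9.1.1 to Section 14.1 at the same time.

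Optionally, and for information only, report that the chance of at least one false go across the two stratum tests and the pooled test is about 6% (0.0628 without the look) when both rates are 15%. The protocol claims no familywise control, so this is not an error.

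The cost is wording and recalculated figures; no extra patients are needed.

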14.2 Statistical Methods

All analysis will be performed in accordance with a detailed Statistical Analysis Plan (SAP).

14.2.1 Analysis Populations

The primary analysis will be performed on the evaluable population. The evaluable population will consist of all enrolled patients who receive at least one dose of antroquinonol and have a valid baseline tumor assessment. A valid baseline assessment is defined as a readable scan (one in which the images are of high enough quality to permit accurate assessment of the tumor) performed within 14 (\pm 7) days of the date of first administration of study drug. For the efficacy analysis, enrollment will continue until the target number of evaluable patients has been enrolled.

The full analysis set (FAS) and PPS will be used for supportive efficacy analyses. The FAS will consist of patients in the evaluable population who have at least one post-baseline tumor

assessment. The PPS will consist of patients in the FAS who do not have major protocol violations.

The PK population will consist of patients in the first stage who have an evaluable PK profile, defined as a profile from which at least one of the PK parameters stated as endpoints can be estimated, and no protocol deviations that would affect the PK of antroquinonol.

The PopPK population will consist of patients with at least two plasma concentrations and sufficient and reliable dosing histories.

The Safety population will comprise all patients who are treated with at least one dose of study drug.

The PRO population will consist of all patients who have completed the QoL Questionnaire on Day 0 and on at least one occasion after the first administration of study drug.

14.2.2 Efficacy Analysis

Except for the primary efficacy analysis, there will be no formal statistical testing. All data will be summarized and listed as appropriate. All efficacy endpoints will be evaluated in both the overall (unselected) population and within-stratum.

The primary and secondary efficacy analyses will be based on the independent centralized assessment of medical images. A detailed description of the process is provided in the Independent Review Charter.

14.2.2.1 Primary Efficacy Analysis

The primary endpoint is the PFS rate at 12 weeks, defined as the proportion of patients alive and progression-free at Week 12. Patients will be progression-free if they have no evidence of progressive disease (defined according to RECIST guideline, version 1.1) from the start of treatment to Week 12. An evaluable patient who died from any cause or discontinued the study for any reason without a post-screening or Week 12 tumor assessment will be considered as failing to respond to treatment.

The primary analysis will be performed on the evaluable population as defined in [Section 14.2.1](#). The FAS and PPS (as defined in [Section 14.2.1](#)) will be used for supportive efficacy analyses. The PFS rate together with a two-sided 95% exact confidence interval (CI) will be calculated for the evaluable population, FAS and PPS.

The primary analysis will follow the two-stage procedure as specified in [Section 14.1](#).

